7.2.6.1.7 Relationship to the Study Product and/or Clinical Study Procedure

The Investigator is to determine whether there is a reasonable causal relationship between the occurrence of the AE and exposure to the study product and/or clinical study procedure.

Medical judgment should be used to determine the relationship, considering all relevant factors including the pattern of reaction, temporal relationships, relevant medical history, and confounding factors such as co-medication or concurrent diseases.

The expression “reasonable causal relationship” is meant to convey in general that there are facts or arguments to suggest a causal relationship (ICH E2A, Section IIIA 1).

The relationship assessment for an AE is to be completed using the following definitions as a guideline:

Reasonable Possibility:

According to the reporting Investigator, there is a reasonable possibility (i.e., suggestive evidence or arguments) that there is a causal relationship irrespective of the dose administered between:

- The study product (active or placebo) and the AE.
- The clinical study protocol procedure (e.g., bruising or marks from blood draws, injection related trauma, etc.) and the AE.

A two-point scale (Yes or No response) shall be used for the causality assessment. The Investigator shall be asked to indicate a response to each of the following questions in the eCRF:

- “Do you consider that there is a reasonable possibility that the event may have been caused by the study product?”, and
- “Do you consider that there is a reasonable possibility that the event may have been caused by the study product injection procedure?”

If any of these questions is answered Yes, the AE is considered related.

No Reasonable Possibility:

No suggestive evidence or arguments can be identified regarding a causal relationship between the study product or the clinical study protocol procedure and the AE.

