## 1.5 Safety Assessments

The methods for collecting safety data are described in Section 7.2 of the Clinical Study Protocol.

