### (i) Treatment Emergent Adverse Events (TEAEs)

Adverse events (AEs) are to be monitored throughout the course of the study. The study period for the purpose of AE collection is defined as the period from the signing of a study specific informed consent to study exit for a subject. AEs recorded on the electronic case report forms (eCRFs) will be coded using the Medical Dictionary for Regulatory Activities (MedDRA). AEs will be classified as treatment-emergent adverse events (TEAEs) if the AE had an onset time greater than or equal to the time of the dose of study treatment.

Adverse events endpoints include:

- Incidence,
- Causality (related/not related to investigational product),
- Intensity (mild/moderate/severe),
- Time to onset,
- Duration,
- Leading to study withdrawal,
- Seriousness.

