## 2 Statistical Methods

### 2.1 General Methods

Any change made to the finalized SAP will be documented in the Clinical Study Report (CSR).

Some of the analyses detailed here may be more explicit or in some aspects different from those stated in the protocol. In case of differences, this SAP supersedes the statistical sections in the protocol.

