### 2.5.2 Adverse Events

An overall summary of all AEs will be provided by treatment group, which will include:

- number and percentage of subjects with at least one AE and number of events,
- number and percentage of subjects with at least one TEAE and number of events,
- number and percentage of subjects with at least one treatment-related TEAE and number of events,
- number and percentage of subjects with at least one mild, moderate, and severe TEAE and number of events,
- number and percentage of subjects with at least one TEAE leading to discontinuation and number of events,
- number and percentage of subjects with at least one serious TEAE and number of events.

All TEAEs, serious TEAEs, TEAEs by maximum intensity, TEAEs by causality, TEAEs by maximum intensity and causality, treatment-related TEAEs, and TEAEs leading to discontinuation will be summarized by treatment group, SOC, and PT including number of subjects with at least one event, percentages, and number of events.

For treatment-related AEs, the number of days to onset and duration of event will be summarized by treatment group, SOC, and PT.

Time to onset of an AE will be derived as the start date minus the date of treatment. If the start date is missing, it will be assumed that the AE started on the day of treatment.

Duration of an AE will be derived as the stop date minus the start date + 1. If the start date is missing, it will be assumed that the AE started on the day of treatment. Missing stop date will not be imputed and therefore no duration will be calculated in these cases.

For subject counts, a subject will only be counted once per SOC and once per PT in cases where multiple events are reported for a subject within SOC or PT. For event counts, subjects with multiple events in a category will be counted for each event.

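### Does the SAP leave open whether an adverse event blamed only on the injection procedure counts as treatment-related?

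*SAP*

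**What the plan says.** Protocol 7.2.6.1.7 puts two Yes/No questions in the eCRF for every adverse event. The first asks whether the study product may have caused it. The second asks whether the event "may have been caused by the study product injection procedure". The combining rule is explicit: "If any of these questions is answered Yes, the AE is considered related".

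SAP 1.6 lists causality among the adverse event endpoints as "Causality (related/not related to investigational product". SAP 2.5.2 then asks for the "number and percentage of subjects with at least one treatment-related TEAE and number of events", for tables by system organ class and preferred term that include "TEAEs by causality, TEAEs by maximum intensity and causality, treatment-related TEAEs", and for onset and duration: "For treatment-related AEs, the number of days to onset and duration of event will be summarized by treatment group, SOC, and PT". No visible SAP sentence says which eCRF answers make an event treatment-related.

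Two SAP statements bear on how the documents fit together. SAP 1.5 states: "The methods for collecting safety data are described in Section 7.2 of the Clinical Study Protocol". SAP 2.1 states: "In case of differences, this SAP supersedes the statistical sections in the protocol".

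**The concern.** The endpoint label in SAP 1.6 names the product alone, and the SAP writes treatment-related where protocol 9.1.3.1 writes related. A programmer working from the SAP alone could derive the flag from the first question and drop every event the investigator attributed only to the injection. That case is foreseeable: protocol 7.2.6.1.7 itself gives trauma from the injection as an example of a procedure-caused event, and every subject is injected, placebo subjects included.

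If two programmers chose differently, the related-event counts, the causality tables and the onset and duration summaries would not agree. In a dose-ranging study a reader may also want to separate product effects, which may vary with dose, from injection effects that all arms share.

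**Working it through.** The plan states no figure on this point, so the check is a comparison of texts plus two counts.

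**Step 1: classify the four answer pairs** (product answer / procedure answer).

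| Pair | Protocol 7.2.6.1.7 | SAP 1.6 label read literally |
|---|---|---|
| Yes / Yes | related | related |
| Yes / No | related | related |
| No / No | not related | not related |
| No / Yes | related | not related |

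The readings differ in 1 of 4 pairs. This counts categories and says nothing about how often such events occur.

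**Step 2: count the outputs in SAP 2.5.2 that use relatedness.** The overall summary has 6 rows, of which 1 depends on it (at least one treatment-related TEAE). There are 7 summaries by system organ class and preferred term, of which 3 depend on it (by causality, by maximum intensity and causality, treatment-related). The 2 summaries of onset and duration also depend on it. The other 6 − 1 = 5 rows and 7 − 3 = 4 tables do not.

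**Step 3: ask which rule governs the flag.**

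- Protocol 7.2.6.1.7 is the only visible text that says how to turn the two answers into a classification. The SAP 1.6 entry is a short item in a list of endpoints; it does not tell anyone to use the first answer and ignore the second.
- SAP 1.5 points to protocol Section 7.2, where that rule sits. The pointer is to collection methods, but the relatedness assessment is part of that section.
- The precedence clause in SAP 2.1 reaches the protocol's statistical sections. The relatedness rule stands in Section 7, outside them, so it is not displaced.
- Protocol 9.1.3.1 lists related TEAEs, TEAEs by causality, TEAEs by maximum intensity and causality, and onset and duration of related TEAEs. SAP 2.5.2 carries these outputs over almost unchanged and adds a table of treatment-related TEAEs. The natural reading is the same flag under a longer name.
- Protocol 6.3.4 describes the treatment as an injection given by the investigator, so treatment-related can readily cover the act of injecting.

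Each point leads to the either-question rule, and no visible instruction leads elsewhere.

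**Step 4: ask what a different choice would change.** SAP 2.5 plans no inference on safety. SAP 2.1.2 puts all eCRF data and derived variables into listings, so both answers remain open to inspection. If no event is answered No / Yes, the two readings give identical tables.

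**The case for a change.** The best argument for a change is that the SAP should carry its own definition. Protocol 7.2.6.2.1 speaks of events related to the treatment or to a study procedure as two different things, which supports a product-only reading of treatment-related. SAP 1.5 refers to how data are collected, not to how analysis flags are derived. Since SAP 2.1.1 requires validation by independent programming, one stated derivation would be useful.

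Part of this stands: the wording is not reconciled in the visible text, and a pointer to 7.2.6.1.7 would be tidier. But the contrast in 7.2.6.2.1 is weaker than it looks. Protocol 7.2.6.1.7 counts marks from blood draws among study procedures, so that term is wider than the injection procedure in the second eCRF question and does not put the injection outside the treatment.

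A request for separate product-related and procedure-related tables would correct no stated rule. The comparison they would serve is already available: placebo is also given in the glabellar region, and all TEAEs are summarized by treatment group whatever their causality. SAP 2.1.2 also allows supportive analyses to be added without an amendment.

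Nor can the effect be sized by the weight of one subject. One subject in an 80-subject dose group is 1/80 = 1.25 percentage points, but that holds for any row of any safety table. The documents give no rate of procedure-only events from which to go further.

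**Conclusion.** The literal mismatch is real but confined to one answer pair, and the documents supply the rule that resolves it. An analyst who reads the SAP with the protocol would class a No / Yes event as related and produce sound tables. This is a loosely worded label and a detail left to the protocol, so no change to the plan is needed.

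Its reach is 1 of 6 overall rows, 3 of 7 tables by system organ class and preferred term, and the onset and duration summaries, all descriptive. The conclusion assumes that no unseen text sets a product-only rule. SAP 2.1.3 on data transformations is redacted, the text of SAP 2.9 is not visible, and table formats sit in a companion document; any of these may already define the flag. Whether the redacted DSMC stopping criteria use relatedness cannot be seen, so nothing is inferred from them in either direction.

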### (ii) Neutralizing Antibody Production

[REDACTED]

**(iii) Laboratory Safety Tests**

Hematology and blood chemistry laboratory safety tests will be performed [REDACTED]

Laboratory safety test endpoints include:

- Values,
- Changes from baseline.

For each out of range laboratory result, the Investigator or designee will assess for clinical significance. All clinically significant out-of-range laboratory values for blood samples collected at baseline will be recorded in the medical history. All clinically significant out-of-range laboratory values for blood samples collected after baseline are to be reported as an AE if this abnormality was not present at the baseline visit or is assessed as having worsened since the baseline visit (i.e. there is a significant change from baseline). In instances when a laboratory abnormality is reported, the Investigator is to provide a diagnosis rather than reporting individual laboratory abnormalities, whenever possible.

**(iv) Focused Physical Examination**

Investigator or designee will perform a physical examination of the subject that includes the face and neck. The Investigator may choose to investigate any other sign that he/she observes during the physical examination and should assess all abnormal findings for clinical significance.

**(v) Vital Signs**

Vital signs (including blood pressure, heart rate, and respiratory rate) will be evaluated [REDACTED]

Vital signs endpoints include:

- Values,
- Changes from baseline.

All abnormal values at the screening visit identified as clinically significant by the Investigator will be recorded in the medical history.

For any clinically significant changes from the screening visit, an AE is to be recorded.

Normal ranges checks, as programmed in the eCRF to alert the investigator to assess clinical significance for values outside of these ranges, are shown in Table 4 below.

**Table 4. Vital Sign Normal Ranges**

Measure	Normal Range
Sitting Systolic blood pressure	90-150 mmHg
Sitting Diastolic blood pressure	60-90 mmHg
Sitting Heart rate	50-100 beats/min
Sitting Respiratory rate	12-24 breaths/min

## 2 Statistical Methods

### 2.1 General Methods

Any change made to the finalized SAP will be documented in the Clinical Study Report (CSR).

Some of the analyses detailed here may be more explicit or in some aspects different from those stated in the protocol. In case of differences, this SAP supersedes the statistical sections in the protocol.

#### 2.1.1 Programming Conventions

EMB Statistical Solutions will have responsibility for performing analyses. All computations for statistical analyses will be performed using SAS® software, Version 9.4 or later. All SAS programs used in the production of statistical summary outputs will be validated with independent programming prior to finalization. In addition, all program outputs will be independently reviewed. The validation process will be used to confirm that all data manipulations and calculations were accurately done. Once validation is complete, a senior statistical reviewer will perform a final review of the documents to ensure the accuracy and consistency with this plan and consistency within tables. Upon completion of validation and quality review procedures, all documentation will be collected and filed by the project statistician or designee.

The eCRF data for all subjects will be provided in Standard Data Tabulation Model (SDTM) datasets. Analysis Data Model (ADaM) datasets will be developed from the SDTM datasets for use in table and figure production.

#### 2.1.2 Reporting Conventions

The formats for the tables, listings, and figures described in this SAP will be provided in a companion document. Changes to the formats of these reports that are decided after the finalization of the SAP will not require an amendment. In addition, any additional supportive or exploratory analyses requested after SAP approval will not require amendment of the SAP. These additional analyses will be described in the CSR.

All study data from the eCRFs as well as derived variables will be provided in subject data listings. An indication of specific listings for each data type will not be indicated in the text of subsequent SAP sections. Data listings supplied as part of the CSR will be sorted by treatment group, study center number concatenated with subject number, assessment dates, and/or time point.

The following conventions will be applied to all data presentations and analyses:

- Placebo-treated subjects will be pooled together in summary tables and for analyses.
- Treatment groups to be summarized include [REDACTED] abobotulinumtoxinA and pooled placebo.
- Quantitative variables will generally be summarized by the number of subjects, mean, standard deviation, median, Q1, Q3, minimum, and maximum. Unless otherwise specified, the minimum and maximum values will be displayed to the same number of decimal places as the raw data, the mean and median will be presented to one extra decimal place compared to the raw data, and the standard deviation will be displayed to two extra decimal places compared to the raw data.

- Categorical variables will be summarized by the number and percentage of subjects within each category. Unless otherwise specified, the percentage will be presented in parentheses to one decimal place. Frequency and percentage values of 0 will be presented as '0' rather than '0 (0)'.
- All summary tables will include the analysis population sample size (i.e. number of subjects) in each treatment group.
- Date variables will be formatted as DDMMYY for presentation.

### 2.1.3 Data Transformations

[REDACTED]

[REDACTED]

## 2.2 Analysis Populations

The statistical analyses will be performed based on the following subject populations.

### 2.2.1 Intent-to-treat Efficacy Population

The Intent-to-treat (ITT) population includes all subjects who are randomized and dispensed (i.e., administered) the investigational product, and will be analyzed according to the randomization scheme. All primary efficacy, secondary efficacy, and exploratory variables will be analyzed based on the ITT population.

### 2.2.2 Per-Protocol Efficacy Population

The Per-Protocol (PP) population includes all ITT subjects who have no protocol deviations considered to have a substantial impact on the primary efficacy outcome, and will be analyzed according to the randomization scheme. If the PP population contains less than 90% of the subjects in the ITT, a sensitivity analysis of the primary efficacy endpoint will be performed based on the PP population.

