5 SELECTION AND DISPOSITION OF CLINICAL STUDY POPULATION

5.1 Number of Subjects

Approximately 400 subjects will be enrolled. In each treatment group, 80 subjects will be treated with abobotulinumtoxinA, and 20 subjects will be treated with placebo.

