### 1.1.2 Number of Subjects and Randomization

The study is planned to enroll approximately 400 subjects who will be treated with [REDACTED] abobotulinumtoxinA (approximately 80 subjects/dose) or placebo (up to 80 subjects depending on the number of dose groups that will run in the study).

Initially, eligible subjects will be randomly assigned at baseline to one of the following treatment

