### 2.3.2 Protocol Deviations

Subjects with any protocol deviations will be summarized by study center and in total (by treatment group and overall).

Depending on the seriousness of the deviation, a subject might be excluded from the PP population, which shall be documented prior to database lock. Since the PP population will be used for the primary analysis at Month 1 only, the focus will be on major deviations occurring before and on the Month 1 visit which are considered to have a substantial impact on the primary efficacy outcome. Reasons for exclusion from the PP population will be presented by treatment group and overall.

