## 2.4 Efficacy Analysis

### 2.4.1 Datasets Analyzed

All efficacy variables will be analyzed based on the ITT population. A sensitivity analysis of the primary efficacy endpoint will be performed based on the PP population. Summary statistics will be computed for each efficacy endpoint using the Observed Cases (OC) with no imputation for missing

data. Inferential statistical analyses will account for missing data as appropriate (SAP Section 2.4.2 below).

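### Does the SAP leave open whether the per-protocol sensitivity analysis is run when PP is 90% or more of ITT?

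*SAP*

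**What the plan says.** Three places in the SAP bear on the PP analysis.

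- **SAP 2.2.2 (Per-Protocol Efficacy Population)** defines the PP set, which "includes all ITT subjects who have no protocol deviations considered to have a substantial impact on the primary efficacy outcome". It then gives a numerical trigger: "If the PP population contains less than 90% of the subjects in the ITT, a sensitivity analysis of the primary efficacy endpoint will be performed" on that set. It does not say what happens at 90% or more.
- **SAP 2.4.1 (Datasets Analyzed)** says: "A sensitivity analysis of the primary efficacy endpoint will be performed based on the PP population". It gives no condition and does not refer back to 2.2.2.
- **SAP 2.3.2 (Protocol Deviations)** opens a sentence with "Since the PP population will be used for the primary analysis at Month 1 only" and goes on to confine attention to major deviations up to and including that visit. It requires exclusions from PP to be documented before database lock, and reasons for exclusion to be shown by treatment group.

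SAP 2.2.1 and 2.4.1 both make ITT the basis for all efficacy variables. The only visible precedence rule, in SAP 2.1, ranks the SAP above the protocol: "In case of differences, this SAP supersedes the statistical sections in the protocol". It does not rank one SAP section above another.

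**The concern.** A plan should settle in advance which analyses of the primary endpoint will be reported. When PP is at least 90% of ITT, one analyst could omit the PP analysis and cite 2.2.2, while another could run it and cite 2.4.1. Nothing visible says which is right.

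SAP 2.1.2 adds to the unease, because "any additional supportive or exploratory analyses requested after SAP approval will not require amendment of the SAP". The PP result could then be added or left out after the results are known, without an amendment. Fixing PP membership before lock settles who is in the set, but not whether its result is shown. At stake is selective reporting of one supportive analysis.

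**Working it through.** **Inputs.** The trigger is PP < 0.90 × ITT (SAP 2.2.2). Planned enrollment is about 400 (SAP 1.1.2; Protocol 5.1 and 9.2). I assume ITT equals planned enrollment. The documents state no figure for this point that could be reproduced, and they give no expected exclusion rate.

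**Step 1: where the sections differ.** 0.90 × 400 = 360.

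| Exclusions | PP / ITT | SAP 2.2.2 | SAP 2.4.1 |
|---|---|---|---|
| 40 | 360/400 = 90.00% | not triggered, silent | run |
| 41 | 359/400 = 89.75% | run | run |

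The sections differ at 0 to 40 exclusions and agree from 41.

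**Step 2: smaller trials.** SAP 1.1.2 allows placebo numbers to vary ("up to 80 subjects depending on the number of dose groups that will run in the study"). Protocol 5.1 gives, per treatment group, "80 subjects will be treated with abobotulinumtoxinA, and 20 subjects will be treated with placebo", which is 80 + 20 = 100. Three groups would give ITT 300 and a boundary between 30 exclusions (270/300 = 90.00%) and 31 (269/300 = 89.67%). This is 10% of N again and adds nothing new.

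**Step 3: how likely the unsettled case is.** If each subject is excluded independently with an assumed probability d, the trigger is met with probability P(X ≥ 41), where X ~ Binomial(400, d).

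| Assumed d | P(X ≥ 41) |
|---|---|
| 5% | 0.00 |
| 8% | 0.06 |
| 10% | 0.46 |
| 12% | 0.88 |
| 15% | 1.00 |

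This is a range, not a forecast. At 8% or below, the case that 2.2.2 leaves unstated is the likely one, so the ambiguity is not confined to a remote corner.

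**Step 4: what each reading produces at 90% or more.**

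- *2.2.2 governs, and 2.4.1 restates it briefly.* No PP table is required. The report still gives the ITT result, the multiple-imputation repeat of the primary endpoint (SAP 2.4.2), PP counts by treatment group (SAP 2.3.1) and reasons for exclusion (SAP 2.3.2).
- *2.4.1 governs.* One supportive table is added. This does not breach 2.2.2, which says when the analysis must be run and does not prohibit it otherwise.

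The ITT analysis, the comparison with placebo, alpha and power are the same in both.

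**Step 5: the weight of SAP 2.3.2.** Its sentence explains which deviations matter for exclusion. It calls the PP use the primary analysis, although 2.2.1 puts the primary analysis on ITT, so the wording is loose. It is background and not a second commitment to run the analysis. The mismatch rests on the single sentence in 2.4.1.

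**The case for a change.** The strongest case for acting is that the two sentences are almost identical apart from the condition, so they plainly govern one analysis. Two competent programmers could deliver different table sets and each cite the SAP. The open zone is wide, and aligning the sentences would cost next to nothing. The 90% cut also applies to the total, so a PP set above it could still hide exclusions concentrated in one arm.

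The textual point stands: the sections are not aligned, and the precedence rule does not help. The consequence drawn from it is weaker.

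- A specific numerical condition ordinarily governs a general restatement, so there is a natural way to read the sections together.
- Whether PP falls below 90% is a count, and it is fixed once exclusions are documented before lock. It does not depend on outcome results.
- Counts and reasons for exclusion by treatment group are reported either way. Uneven exclusions would be visible, and so would an analysis omitted despite the trigger.
- The freedom in SAP 2.1.2 to add supportive analyses exists whether or not 2.2.2 and 2.4.1 agree, and additions must be described in the study report. Aligned wording would not remove it.

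**Conclusion.** The concern does not call for a change. SAP 2.2.2 and 2.4.1 differ in wording over 0 to 40 exclusions with ITT taken as 400, and the visible text does not say which governs there. This is an editorial inconsistency that analysts can resolve sensibly, either by applying the specific rule or by running the analysis in every case. What varies is the presence of one supportive table. The ITT primary result, alpha, power and the trial's conclusion are unaffected, so tidying the sentences would bring no statistical gain.

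The conclusion assumes that ITT is close to planned enrollment and that exclusions are documented before lock, as SAP 2.3.2 requires. It is limited to the visible text. The protocol's efficacy-population text is redacted, the SAP primary-analysis section breaks off, and SAP 2.9 is listed in the contents but not shown. Any of these could already settle the point.
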